9.9. Quality control

Aetion will build measures for cohort inclusion, outcomes and covariates based on codes and algorithms described in this protocol, which were collaboratively agreed upon with Pfizer. All measures created, cohorts developed, statistical analyses implemented, and tables completed will undergo quality control review by at least one additional analyst or scientist under the supervision of the Science Lead. All analyses will separately be doubly implemented by an independent team. Results of single and double implementations will be compared, and any discrepancies will be adjudicated by a third-party senior science team

member not involved in either implementation. Furthermore, the Science Lead will review all results tables to confirm accuracy, logical flow, and appropriate format. This protocol will be strictly followed when conducting the analysis of this study.

The data were subject to quality control procedures. The data provider was contacted to help rectify any problems identified during the quality control procedures, including if the files received appeared to be incomplete or the data values were implausible. The data are loaded into the Aetion Evidence Platform after minimal processing into patient longitudinal timelines to enable representation of the original data and without any data loss. Events are required to have a valid start date. Record counts are cross-checked for validation and compared to the original data counts.

9.10. Strengths and limitations of the research methods

This study has several strengths. It is a population-based study, and while the use of IV pantoprazole in infants aged 1 month to <1 year and patients aged 1 to <2 years is rare, this database includes a relatively large number of IV pantoprazole users in these age groups, facilitating generation of precise incidence rates. Given the age of the study population, it is less likely that patients will seek health care outside of the Optum EHR system during the baseline period, and therefore, it is less likely that an outcome of interest occurring during the baseline period will be missed; thus prevalent conditions are unlikely to be mistaken for incident events. Similarly, given the relatively short follow up time, it is less likely that patients will seek care outside of the Optum EHR system during this period, and therefore, that incidence events will be missed.

The study also has several limitations. As is the case in any administrative claims-based study without outcome validation/adjudication, outcome misclassification is a possibility. Diagnosis codes may be incorrect, or may be included as part of the diagnostic rule-out process rather than an indication of diagnosis itself. Conditions not requiring treatment or office visits tend to be systematically undercoded in such databases. It is possible that this study will only capture severe manifestations of such disorders. However, this limitation is likely to be applicable to two outcomes of interest -vomiting and diarrhea as patients experiencing these symptoms may not always visit a physician for care. Another well-recognized limitation of claims database analysis is that the gap between disease onset and date of diagnosis. However, in an incidence analysis, the time at risk begins on the date of IV pantoprazole administration (ie index date), not at disease onset. For outcome events, as only the incidence of new events is considered that occur after the initiation of IV pantoprazole, the impact of this limitation is expected to be minimal, as complications arising in infants would almost certainly be captured in the inpatient setting. Additionally, this would result in underestimating the incidence rate as time at risk would be inflated.

More sensitive algorithms will be employed (i.e. algorithms based only on diagnostic codes, rather than more specific algorithms employing procedure and treatment codes in addition to diagnostic codes) for capturing outcomes to ensure safety events of interest are not missed.

However, the limitation of this approach is that, the incidence of some outcomes may be overestimated. Infants with a diagnosis of GERD with EE may be misclassified as those without EE. This is because a confirmed diagnosis of GERD with EE may not be available in infants due to reluctance of healthcare professionals to seek a confirmation via endoscopy. Also, those with a presumptive diagnosis of EE may be classified into the subset of infants with GERD alone. Prior to October 2015, ICD-9-CM codes were exclusively used to identify eligible patients, and GERD is not explicitly captured under this coding schema. ICD-10-CM codes provide additional granularity, but a validated code for erosive esophagitis and GERD is not available, nor well-established or validated in the literature. However, including patients identified using both coding schemes is important to increase sample size of this small population of pediatric patients with a rare condition and exposure. To examine the impact of different coding systems, a sensitivity analysis stratified by those patients identified via ICD-9-CM codes versus ICD-10-CM codes, respectively is planned. The counts of the top 25 most common conditions occurring within 30 days prior to or on the index date through 90 days of the last treatment with IV pantoprazole may include prevalent/comorbid conditions and not just conditions emerging following IV pantoprazole administration. This will however help generate hypotheses about unsuspected safety events in this patient population. Furthermore, a pre-planned sensitivity analysis stratifying by each code type will be performed for the analysis to understand if significant heterogeneity exists in this patient population with respect to the incidence of these outcomes following administration of IV pantoprazole. Finally, the study results may not be generalizable to infants aged 1 month to <1 year and patients aged 1 to <2 years outside of the commercially insured population.

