9.4.2. Outcomes of interest

The outcomes of interest are listed in Table 3 below. These outcomes were based on the Investigator's Brochure (version 4.0 June 2021) and expert clinical judgment. The first occurrence of each outcome is defined based on the presence of at least one ICD-9-CM or ICD-10-CM diagnosis code identified in the inpatient or outpatient setting during the follow-up period.

Outcome of interest	Operationalization: ICD-10-CM code	Operationalization: ICD-9-CM code
Agranulocytosis	D70.2 Other drug-induced agranulocytosis D70.1 Agranulocytosis secondary to cancer chemotherapy	288.03 Drug induced neutropenia
Thrombocytopenia	D69.3 Immune thrombocytopenic purpura D69.59 Other secondary thrombocytopenia D69.6 Thrombocytopenia, unspecified D69.41 Evans syndrome D69.49 Other primary thrombocytopenia	287.31 Immune thrombocytopenic purpura 287.49 Other secondary thrombocytopenia 287.5 Thrombocytopenia, unspecified 287.30 Primary thrombocytopenia, unspecified 287.32 Evans syndrome 287.39 Other primary thrombocytopenia
Leukopenia	D72.810 Lymphocytopenia D72.818 Other decreased white blood cell count D72.819 Decreased white blood cell count, unspecified D70.8 Other neutropenia D70.9 Neutropenia, unspecified D70.0 Congenital agranulocytosis	288.51 Lymphocytopenia 288.59 Other decreased white blood cell count 288.50 Leukocytopenia, unspecified 288.09 Other neutropenia 288.00 Neutropenia, unspecified
Pancytopenia	D61.811 Other drug-induced pancytopenia	284.12 Other drug-induced pancytopenia
	D61.818 Other pancytopenia	284.19 Other pancytopenia

Hypersensitivity (including anaphylactic reactions and anaphylactic shock)	K52.2x Allergic and dietetic gastroenteritis and colitis M31.0 Hypersensitivity angiitis T78.2x Anaphylactic shock, unspecified T78.4x Other and unspecified allergy M36.4x Arthropathy in hypersensitivity reactions classified elsewhere	558.3 Allergic gastroenteritis and colitis 446.20 Hypersensitivity angiitis, unspecified 446.21 Goodpasture's syndrome 446.29 Other specified hypersensitivity angiitis 995.0 Other anaphylactic reaction, Not elsewhere classified (NEC) 995.3 Allergy, unspecified, NEC 713.6 Arthropathy associated with hypersensitivity reaction
Hyperlipidemia	E78.49 Other hyperlipidemia E78.5 Hyperlipidemia, unspecified	272.4 Other and unspecified hyperlipidemia
Hypertriglyceride mia	E78.1 Pure hyperglyceridemia	272.1 Pure hyperglyceridemia

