For analyses of estimation of incidence rates of the outcomes of interest during follow-up, each analysis will be restricted to patients without a history of outcome of interest prior to the index date (ie baseline period); thus, for each analysis of a given specified outcome, a distinct sub-cohort will be used (i.e. for the estimation of the incidence of hepatitis, only patients with prevalent cases of hepatitis in the baseline period will be excluded from follow-up and will not contribute to person-time at risk).

For each outcome of interest, patients will be followed from the index date to whichever of the following occurs first (follow-up period):

- Occurrence of an outcome of interest,
- 90 days following the discontinuation of IV pantoprazole administration,
- Initiation of a separate IV pantoprazole infusion within 90 days following the discontinuation of IV pantoprazole administration, where a separate infusion is defined as the subsequent administration at least 7 days from the end of the previous infusion,
- Death,
- End of enrollment in the database,
- End of study period (ie, 31 December 2020).

Incidence rates of each prespecified outcome of interest will be estimated as the number of patients with a specific outcome of interest during the follow-up period divided by the total person-time at risk and reported as incidence per 1,000 person-years with associated 95% CIs, assuming a Poisson distribution. Exact Poisson confidence limits for the estimated rate are found as the Poisson means, for distributions with the observed number of events and probabilities relevant to the chosen confidence level, divided by time at risk.

$$egin{aligned} Y_l &= rac{\chi^2_{2Y,\;lpha/2}}{2} \ Y_u &= rac{\chi^2_{2(Y+1),\;1-lpha/2}}{2} \end{aligned}$$

- where Y is the observed number of events, Yl and Yu are lower and upper confidence limits for Y respectively, $\chi 2\nu$, a is the chi-square quantile for upper tail probability on ν degrees of freedom.

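### Section 9.10 gives coding delay only a downward bias, but events are dated by first code, so conditions that began before IV pantoprazole and were coded afterwards raise the rates, and the bias can go either way

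*Protocol*

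**What the plan says.** Section 9.10 of the protocol raises the issue itself: "Another well-recognized limitation of claims database analysis is that the gap between disease onset and date of diagnosis". It then sets the issue aside as having little effect. The reason given is that the analysis counts only events arising once treatment has started, supported by the expectation that "complications arising in infants would almost certainly be captured in the inpatient setting". It closes with the only direction of bias attached to this limitation: "Additionally, this would result in underestimating the incidence rate as time at risk would be inflated".

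Earlier in 9.10, among the strengths, the protocol argues that children of this age are unlikely to seek care elsewhere during baseline, "thus prevalent conditions are unlikely to be mistaken for incident events".

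The operational rules are in two other places. Section 9.4.2: "The first occurrence of each outcome is defined based on the presence of at least one ICD-9-CM or ICD-10-CM diagnosis code", in the inpatient or outpatient setting during follow-up. Section 9.8: "each analysis will be restricted to patients without a history of outcome of interest prior to the index date (ie baseline period"), and "For each outcome of interest, patients will be followed from the index date to whichever of the following occurs first (follow-up period").

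**The concern.** The reassurance in 9.10 depends on counting only events that are new after treatment starts. The rules in 9.4.2 and 9.8 never use an onset date, so what is counted is events newly coded after treatment starts. The two differ exactly when there is a gap between onset and code, which is the limitation under discussion. A child whose condition was present before the first infusion, but whose first code came days later, has no baseline history, enters the risk set and is counted as an incident case.

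Table 3 contains codes for which this is easy to picture. Leukopenia includes congenital agranulocytosis, and hepatobiliary injury includes chronic hepatitis, chronic hepatic failure and cirrhosis. Exposure is found from inpatient codes (9.4.1), so a diagnostic work-up may well be in progress at the index date.

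The study has no comparator (9.1), so each rate must be read in absolute terms, and the stated direction of bias guides that reading. Neither analysis in Table 6 examines the point. One drops the 30-day enrollment requirement, which can only admit children with a shorter baseline. The other splits by coding system.

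**Working it through.** **The plan's own figure.** The point disputes no number in the protocol. The illustration borrows one row of Table 5: 1% of 7,489 infants, rounded to 75 events. The Wilson interval for 75/7,489 has centre term 0.01001 + 0.00026 = 0.01027, half-width term 1.96 × 0.001158 = 0.00227 and divisor 1.0005. This gives 0.0080 to 0.0125, as printed.

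**Inputs from the protocol.** N = 7,489 and x = 75 (9.6, Table 5); follow-up from the index date to 90 days after discontinuation unless another stop comes first (9.8); rate = patients with the outcome ÷ person-time (9.8).

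**Assumptions not in the documents.** D = 93 days of follow-up per child with no other censoring; a fixed lag L = 7 days from onset to code (3 and 14 days as a range); onsets spread evenly over time; h = onset hazard just before index divided by onset hazard after index.

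**Baseline.** Person-time = 7,489 × 93 / 365.25 = 1,907 person-years. Rate = 75 / 1,907 = 39.3 per 1,000 person-years.

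**Effect 1: inflated time at risk, the only one 9.10 names.** Each of 75 events adds 7 days: 75 × 7 / 365.25 = 1.44 person-years. 1.44 / 1,907 = 0.075%, so the rate falls by about 0.1%.

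**Effect 2: onsets in the last L days of follow-up, coded after it ends.** Lost events = 75 × 7/93 = 5.6. 5.6 / 75 = 7.5%, so the rate falls by about 7.5% (3-day lag: 3/93 = 3.2%; 14-day lag: 14/93 = 15.1%).

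**Effect 3: onsets in the L days before index, coded after it.** Added events = h × 75 × 7/93 = 5.6 × h.

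**Net.** Leaving aside the small changes in person-time, the relative change in the rate is about (L/D) × (h − 1). At L = 7 and D = 93:

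| h | Added (effect 3) | Lost (effect 2) | Net change in rate |
|---|---|---|---|
| 0 | 0 | 5.6 | −7.5% |
| 0.5 | 2.8 | 5.6 | −3.8% |
| 1 | 5.6 | 5.6 | 0% |
| 2 | 11.3 | 5.6 | +7.5% |
| 5 | 28.2 | 5.6 | +30% |
| 10 | 56.5 | 5.6 | +68% |

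The effect that 9.10 names is the smallest of the three. The sign of the total depends on h, about which the documents say nothing.

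**The case against.** The sentence in 9.10 follows a clause about events arising after initiation, and for those events delayed coding does lower the rate. Within that scope it is incomplete rather than false. This stands as far as it goes, but the limitation being discussed is the gap between onset and diagnosis in general, and the design cannot restrict itself to true post-index onsets.

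Prevalent disease is handled in part, because 9.3.1 and 9.8 remove children with a recorded history of the outcome. Section 9.10 also warns of incorrect and rule-out codes and says that some outcomes may be overestimated. A reader is therefore told that rates can be too high. Those warnings concern miscoding and the use of code-only algorithms, however, and the remark about prevalent conditions rests on care outside the system being unlikely. None of them covers coding delay.

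A reader might infer that the rates are too high overall. The documents do not support that. Onsets coded after follow-up ends are lost, the two effects cancel when the hazard is equal before and after index, and any assumed share of pre-index onsets is an input. For example, assuming that 0.1% of infants have such an onset adds 7.5 events, an apparent +10%. After subtracting the 5.6 lost events the net is (7.5 − 5.6)/75, about +2.5%.

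A reader might also infer that the remark about inpatient capture contradicts 9.4.2, which counts outpatient codes too. It is an expectation about where complications appear and does not define the outcome. It gives weak support for calling the impact minimal, but it is not a contradiction.

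Finally, a lagged analysis drops true early reactions, and a 7-day lag would start the clock after a course of fewer than 4 consecutive days had ended. That limits which outcomes and which lag are sensible. It does not rescue the sentence in 9.10.

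**Conclusion.** The point holds as a misstatement of the direction of bias. Dating events by first code and removing prevalent cases only by prior record lets pre-index conditions enter as incident events, and 9.10 does not say so. The mechanism it does name is worth about 0.1% of the rate at a 1% outcome frequency and a 7-day lag. Loss of late-coded onsets is worth about −7.5% under the same lag and 93 days of follow-up. Entry of pre-index onsets works upward, and the net is upward whenever onset hazard is higher before index than after. A raised hazard around the start of inpatient treatment is plausible but is not quantified in the protocol. The lag, follow-up length and hazard ratio are all assumptions, so the figures show relative size and sign only. The primary analysis need not change. What changes is how its absolute rates may be read.

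**What to change.** 1. In 9.10, replace the sentence on underestimation with a statement that coding delay can bias rates in either direction: downward through added person-time and through onsets coded after follow-up ends, and upward when onset precedes the index date but the first code follows it.
2. Qualify the statement in 9.10 that prevalent conditions are unlikely to be taken for incident ones, so that it covers care outside the system and not coding delay.
3. Report, for each outcome and cohort, the distribution of days from index to first code. Clustering in the first days would flag outcomes where pre-index onset is a concern, although it cannot separate this from a rapid drug effect.
4. Add a row to Table 6: a sensitivity analysis in which events and person-time start a short lag after index (for example 2 days), with children coded within the lag removed for that outcome. Limit it to non-acute outcomes such as the hepatobiliary, hematologic and lipid ones, and say why: it discards true immediate reactions such as anaphylaxis, urticaria, angioedema and injection-site events.

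The cost is a few sentences, one descriptive table and one re-run of existing code with a shifted start. A short lag removes only pre-index onsets coded within it, so the result should be read beside the table in item 3. Moving index-date codes into baseline would not be a substitute, because the problem lies in codes dated after the index date.

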9.11. Other aspects

Not applicable

10. PROTECTION OF HUMAN SUBJECTS

10.1. Patient information

This study involves data that exist in anonymized structured format and contain no patient personal information.

10.2. Patient consent

As this study involves anonymized structured data, which according to applicable legal requirements do not contain data subject to privacy laws, obtaining informed consent from patients by Pfizer is not required.

10.3. Institutional review board (IRB)/Independent ethics committee (IEC)

As this study involves anonymized structured data IRB/IEC review is not required; no IRB waiver was received.

2.0,

Version

10.4. Ethical conduct of the study

10 February 2022

The study will be conducted in accordance with legal and regulatory requirements, as well as with scientific purpose, value and rigor and follow generally accepted research practices described in the FDA Guidance for Industry: Good Pharmacovigilance and Pharmacoepidemiologic Assessment⁶, Guidelines for Good Pharmacoepidemiology Practices (GPP) issued by the International Society for Pharmacoepidemiology (ISPE)⁷, and FDA Guidance for Industry and FDA Staff: Best Practices for Conducting and Reporting Pharmacoepidemiologic Safety Studies Using Electronic Healthcare Data.⁸

11. MANAGEMENT AND REPORTING OF ADVERSE EVENTS/ADVERSE REACTIONS

This study involves data that exist as structured data by the time of study start.

In these data sources, individual patient data are not retrieved or validated, and it is not possible to link (i.e., identify a potential association between) a particular product and medical event for any individual. Thus, the minimum criteria for reporting an adverse event (AE) (i.e., identifiable patient, identifiable reporter, a suspect product, and event) cannot be met.

12. PLANS FOR DISSEMINATING AND COMMUNICATING STUDY RESULTS

Study results will be presented as a final study report describing the two cohorts of interest separately. The study may potentially lead to manuscripts that will be submitted to peer-reviewed scientific journals.

In the event of any prohibition or restriction imposed (e.g., clinical hold) by an applicable competent authority in any area of the world, or if the party responsible for collecting data from the participant is aware of any new information which might influence the evaluation of the benefits and risks of a Pfizer product, Pfizer should be informed immediately.

15. LIST OF FIGURES

None

1. ANNEX 1. LIST OF STAND ALONE DOCUMENTS

None

2. ANNEX 2. ENCEPP CHECKLIST FOR STUDY PROTOCOLS

Not applicable

